## Adjustment of ranking criteria for JRT for withdrawals not due to death

In order to test the sensitivity of handling withdrawals not due to death, ranking criteria will be adjusted as a sensitivity analysis for JRT. Instead of 2 categories, subjects will be grouped into 3 categories:

- Group 1: Participants who complete Day 183 and have data available or complete the study but don't have an evaluable result for Day 183
- Group 2: Participants who withdraw from the study due to reasons other than death and don't have Day 183 data available
- Group 3: Participants who die will be ranked based on the time of death

Subjects will be ranked as follows:

• Participants in Group 3 will be given lower ranks than subjects in Groups 1 and 2, with the lowest ranks being given to the subjects who die in the shortest time after first dose. Progressively higher ranks will be given to subjects who die at longer times after first dose.

Product: Nusinersen	Statistical Analysis Plan
Study: 232SM203	Version: 3.0 Final

- Participants in Group 2 will rank lower than subjects in Group 1, with the lowest ranks being given to the subjects who withdraw from the study in the shortest time after first dose. Progressively higher ranks will be given to subjects who withdraw from the study at longer times after first dose.
- Subjects in Group 1 will rank higher than subjects in Groups 2 and 3. Progressively higher ranks will be given to subjects with a higher change from baseline at Day 183 i.e. smaller decline at Day 183.

The same approach using the joint rank test with MI will be implemented for the analysis. The main difference is that the imputed values will only be utilized for ranking if the participant is in group 1. Otherwise, the ranking will be performed based on time in study.

#### Adjustment of ranking criteria for JRT for permanent ventilation

In order to examine the impact of considering permanent ventilation in evaluation of this endpoint the ranking criteria will be adjusted as sensitivity analysis for JRT. Subjects will be grouped into 2 categories:

- Group 1: Participants who complete Day 183 and have data available or reach beyond Day 183 and don't have an evaluable result for Day 183
- Group 2: Participants who die or are confirmed to have met permanent ventilation, i.e. tracheostomy or 22nd day of ventilation is on or prior to Day 183. Participants will be ranked based on the earlier of time of death or time of meeting permanent ventilation definition.

The same approach using the joint rank test with MI will be implemented for the analysis. The main difference is that the imputed values will only be utilized for ranking if the participant is in group 1. Otherwise, the ranking will be performed based on time in study.

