## Joint rank methodology

Death is a potential outcome in the infantile-onset population and the joint rank methodology will be utilized to incorporate both the functional endpoint and mortality.

The joint rank methodology [Berry 2013] allows for a statistical test of the treatment effect on the endpoint while accounting for truncation of data due to deaths. In this analysis, a subject's joint rank score will be calculated by comparing each subject to every other subject in the study, resulting in a score of +1 if the outcome was better than the subject being compared, -1 if worse, and 0 if the same. The subject's score will then be calculated by summing their comparison to all the other subjects in the study.

For the purpose of this calculation, considering an endpoint for change to Day 183, subjects will be grouped into the following 2 categories:

- Group 1: Participants who complete Day 183 and have data available AND subjects who withdraw from the study due to reasons other than death and don't have Day 183 data available
- Group 2: Participants who die will be ranked based on the time of death

The criteria for withdrawals are based on withdrawal from study. A subject may discontinue treatment but still continue in the study and in this case data from assessments conducted after treatment will be included for analysis.

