## Sensitivity analyses

- o Repeated using CS3B sham Day 183 matched to 232SM203 efficacy set (sensitivity)
- Repeated using Greedy matched set (sensitivity)
- Adjustment of ranking criteria for JRT for withdrawals not due to death In order to test the sensitivity of handling withdrawals not due to death, ranking criteria will be adjusted as a sensitivity analysis for JRT These analyses will be performed as described in Section 6.1
- Adjustment of ranking criteria for JRT for permanent ventilation
- Main analysis will be repeated using an ANCOVA model where the variance in each treatment group is estimated separately

In order to examine the impact of considering permanent ventilation in evaluation of this endpoint the ranking criteria will be adjusted as sensitivity analysis for JRT. These analyses will be performed as described in Section 6.1.

• Exclusion of deaths from MI model

The MI model will be run for CHOP INTEND total score for the ITT population excluding data from any subjects who died prior to Day 183, so that missing data for survivors are not influenced by any systematic difference there may be in data from subjects who died. The joint rank analysis will then be conducted using these imputed datasets for survivors and deaths will be ranked the lowest based on time of death. The pvalue from the joint rank analysis with MI will be presented as per the main analysis.

• Data truncated to include only up to and including Day 183

Product: Nusinersen	Statistical Analysis Plan
Study: 232SM203	Version: 3.0 Final

In the event that a participant has CHOP INTEND missing items at Day 183 then data from later visits is utilized as part of interpolation. Some of the subjects in the CS3B study only have data up to Day 183 before the study was stopped in contrast to 232SM203 where all subjects potentially could be followed to Day 302. In order to investigate the sensitivity of the analysis to this truncation an additional analysis will be performed where only the data up to and including Day 183 is utilized from both CS3B and 232SM203 and the item level imputation approach described in Section 6.1 is applied.

- The main analysis will be repeated incorporating Jump to reference in the MI step.
- The main analysis will be repeated for the following subgroups:
  - disease duration
  - baseline CHOP INTEND

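### The permanent-ventilation version of the joint rank test gives no group to participants who withdraw alive before the visit, so it alters the handling of withdrawal as well as of ventilation

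*SAP*

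**What the plan says.** All references are to the Part B infantile-onset SAP.

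**Main analysis.** Section 6.1, Joint rank methodology, puts into Group 1 both completers and "subjects who withdraw from the study due to reasons other than death". The joint rank plus MI text ranks these withdrawals above every death. The primary estimand in Section 6.3.1 says that they are ranked on the imputed Day 183 value.

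**Permanent-ventilation version.** Section 6.1, Adjustment of ranking criteria for JRT for permanent ventilation, allows only two groups:
- The first is "Participants who complete Day 183 and have data available or reach beyond Day 183", the latter being those who lack a usable score at that visit.
- The second, by contrast, is limited to "Participants who die or are confirmed to have met permanent ventilation", ordered by whichever of the two times comes first.
- On imputation, the closing rule is this: "The main difference is that the imputed values will only be utilized for ranking if the participant is in group 1".
- For anyone outside the first group it then adds: "Otherwise, the ranking will be performed based on time in study".

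**Purpose.** Section 6.3.1 gives it as: "In order to examine the impact of considering permanent ventilation in evaluation of this endpoint the ranking criteria will be adjusted".

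**Where it is used.** Tables 4, 7 and 8 (CHOP INTEND, HINE Section 2 and plasma NF-L at Day 183 versus sham) and Tables 9 and 10 (CHOP INTEND and HINE Section 2 at Day 302 versus 12 mg).

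**The concern.** A sensitivity analysis is informative when it changes the one thing it is meant to test. This one is meant to change the status of permanent ventilation. As worded, it also takes away the imputed rank that the main analysis gives to infants who leave the study alive before the visit. If its result differs from the main result, a reader cannot tell whether ventilation or withdrawal caused the difference. A withdrawal for a reason unrelated to the disease could move the result with no ventilation event at all. Withdrawal already has its own sensitivity analysis in the same section.

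**Working it through.** **Step 1: classify each type of participant.**

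| Participant | Main analysis | Withdrawal version (three groups) | Permanent-ventilation version |
|---|---|---|---|
| Completes the visit with data | Group 1, score | Group 1, score | Group 1, score |
| In study beyond the visit, no evaluable score | Imputed value | Group 1, imputed value if study completed | Group 1, imputed value |
| Dies before the visit | Bottom, time of death | Bottom, time of death | Group 2, time of death |
| Meets permanent ventilation, alive | Score or imputed value | Not singled out | Group 2, time of event |
| Withdraws alive before the visit, not ventilated | Group 1, imputed value | Own middle group, above deaths | **Neither group**; imputed value barred; time in study by default |

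The last row is the defect. The closing sentences of the ventilation version are identical to those of the withdrawal version. They fit there because withdrawals have their own time-ranked group. Here the only time-ranked group is death or ventilation.

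**Step 2: the plan's own power figure.** Section 2.3 gives 50 versus 20, a difference of 24 points, SD 8.8, two-sided 0.05, and power of at least about 99%. A two-sample check without deaths: 24 / (8.8 × √(1/50 + 1/20)) = 24 / 2.328 = 10.3, so power is about 1.00. The figure is reproduced. For 50 versus 25 with the 4.5-point gain over 12 mg assumed in the same section: 4.5 / (8.8 × √(1/50 + 1/25)) = 4.5 / 2.156 = 2.09, so power is about 0.55 before deaths are counted.

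**Step 3: simulate with no ventilation events.** Any change then comes from withdrawals alone. Withdrawn survivors are ranked on their own score (main) or on time among the deaths (the literal reading). The test is a t-test on ranks without covariates, with 1,500 to 3,000 runs per scenario. Death levels and withdrawal counts are assumptions; the SAP gives only survival gains of 23% over sham and 3% over 12 mg.

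*Versus sham* (50 versus 20, 24 points, survival 0.93 versus 0.70):

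| Withdrawals, 50/28 mg arm only | Mean-rank difference, main | Ventilation version |
|---|---|---|
| 0 | 29.5 | 29.5 |
| 2 | 29.6 | 27.3 |
| 4 | 29.6 | 24.9 |
| 6 | 29.5 | 22.6 |

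A withdrawn infant's average rank drops from about 47 to 6–8 of 70, but every run stays at p<0.05.

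*Versus 12 mg* (50 versus 25, 4.5 points, SD 8.8). Each cell shows main → ventilation version, with the share of runs at p<0.05 in brackets:

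| Withdrawals (50/28 mg vs 12 mg) | Deaths 12% vs 15% | Deaths 7% vs 10% |
|---|---|---|
| 4 vs 0 | about 9 → 5.1–5.4 (40% → 15%) | 10.2 → 6.4 (49% → 21%) |
| 0 vs 2 | about 9 → 11.3–11.4 (41% → 59%) | 10.0 → 12.2 (47% → 65%) |
| 2 vs 1 | 8.8–9.1 → 8.1–8.4 (40% → 34%) | 10.0 → 9.2 (47% → 41%) |
| 4 vs 2 | 9.0 → 7.6 (39% → 28%) | 10.1 → 8.6 (48% → 36%) |

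Ranges in the middle column come from repeat simulations. The 4.5 and 8.8 are Day 183 planning figures, used here to illustrate Day 302.

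**Step 4: compare with the planned withdrawal version** (12% vs 15% deaths). With 4 versus 0 withdrawals the difference goes from 8.9 (main) to 5.6 (withdrawal version) and 5.2 (ventilation version). With 0 versus 2 it goes from 9.2 to 11.1 and 11.4. The withdrawal version therefore shows 3.3/3.7 = 89% and 1.9/2.2 = 86% of the shift.

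**The case against.** A reader might infer that the plan orders withdrawals to be ranked among the deaths. It does not say so. Group 2 is ranked on time of death or of meeting the ventilation definition, and a live, unventilated withdrawal has neither. The time-in-study sentence may be shorthand for Group 2, since the primary estimand uses similar wording for deaths. On that reading the withdrawal's rank is undefined. This objection stands as to wording, but both readings leave the defect: the imputed value is barred and nothing consistent with the main analysis replaces it.

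A reader might also infer that the primary conclusion is at risk. The figures do not support that: against sham, no simulated run lost significance even with six one-sided withdrawals. The larger shifts versus 12 mg need withdrawals in one arm only. That comparison is randomised and double-blind, and proportional withdrawals move the result much less.

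The withdrawal version is run beside this one in all five tables and would show much of the withdrawal effect. Reasons for withdrawal are tabulated, and time to death or permanent ventilation is analysed separately with withdrawals censored. All of that stands. It lets a careful reader separate the two effects approximately, but it does not make this analysis do what it is stated to do.

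**Conclusion.** The point holds as a wrong rule in a sensitivity analysis. Live, unventilated participants who withdraw before the visit belong to neither group, and the closing rule denies them the imputed rank that the main analysis gives them. A difference from the main result cannot then be attributed to permanent ventilation alone.

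The size is modest. The primary comparison with sham is practically unaffected. The effect matters mainly for the Day 302 comparisons with 12 mg (Tables 9 and 10). There it can go either way, and it ranges from under one rank (2 versus 1 withdrawals) to almost four (4 versus 0) on a difference of about 9 or 10. These figures rest on assumed deaths and withdrawals, on no ventilation events, and on the literal reading that places withdrawals with deaths. The analysis is outside the fixed testing sequence, carries no alpha and cannot change a confirmatory conclusion.

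**What to change.** In Section 6.1, Adjustment of ranking criteria for JRT for permanent ventilation:

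1. Add to Group 1 the participants who withdraw before the visit for reasons other than death and had not met the permanent-ventilation definition by withdrawal. Rank them on their MI value, as in the main analysis.
2. Limit time-based ranking to Group 2 (death or permanent ventilation).
3. Word the rule for each visit where this version is used, Day 302 as well as Day 183.
4. State the assumption that these withdrawals are treated as free of permanent ventilation up to the visit, because their later status is not observed. A middle group, as in the withdrawal version, is a defensible alternative, but it would again change withdrawal handling relative to the main analysis.

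With this change, and no ventilation events, the analysis reproduces the main analysis, as it should. The cost is a sentence or two of SAP text and one line of code, with no new data.

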## Rank based implementation of Joint rank method + MI

As a Sensitivity analysis, a new version of the joint rank test will be implemented, using the change in ranks rather than directly the survival time and change in CHOP INTEND.

Initially, all participants will be ranked based on the baseline CHOP INTEND score, so for the 12 mg versus 50/28mg comparison within 232SM203, with a total of N=75, the lowest score will be ranked as 1 and the highest as 75.

Group 1 will be defined as participants who died prior to Day 183. For this group, ranking will be performed based on Study Day of Death.

Group 2 will be defined as participants who did not die and have either an imputed or observed Day 183 result for total CHOP INTEND.

Product: Nusinersen	Statistical Analysis Plan
Study: 232SM203	Version: 3.0 Final

Subjects will be ranked in each of the 100 MI datasets as follows. The subjects will be ranked for Day 183 with subjects who died in group 1 given a lower rank than subjects in group 2. The subject who died first will be given a rank of 1. For group 2 the lowest Day 183 CHOP INTEND score will be given the lowest rank and the highest CHOP INTEND score will be assigned the highest rank. In the case of ties the mean of the ranks will be assigned to tied subjects

For each of the 100 imputed datasets the change in ranks will be compared between treatment groups using an ANCOVA model. The response variable will be determined as the difference: Rank at Day 183 – \_\_\_\_\_\_. The model will include treatment as a fixed effect and adjusted for each of the corresponding baseline value for the endpoint and, disease duration.

## ANCOVA model

For each of the 100 imputed datasets, the endpoint will be compared between treatment groups using an ANCOVA model for continuous endpoints (primary, secondary and NF-L endpoints). The ANCOVA model will include covariates for each of the corresponding baseline value for the endpoint, baseline CHOP INTEND total score (if not the endpoint under consideration) and disease duration at informed consent. The model will be used to present overall LS means and standard errors for each treatment group, and LS mean differences for treatment with corresponding 95% CI.

## ANCOVA model without equality of variances assumption

As a sensitivity analysis the main analysis will be repeated using the repeated statement in PROC Mixed to estimate the variance for each treatment group separately. For this analysis the degrees of freedom will be adjusted using the Satterthwaite option.

## Jump to reference analysis for MI with the Joint Rank test

Jump to reference (J2R) is a sensitivity analysis such that imputed values for patients in the higher dose arm take on attributes of the reference arm (matched sham subjects) after discontinuation. This is a conservative assumption for the higher dose versus sham comparisons as due to the long half-life it is not likely that following withdrawal the benefit of treatment will completely disappear. J2R analysis will be implemented using the SAS macro RMCONJPLUS (https://www.lshtm.ac.uk/research/centres-projects-groups/missing-data#dia-missing-data}).

In the joint rank step as for the main analysis, for patients who died the ranking will be performed based on day of death and then for patients who have not died the ranking will be based on the change from baseline in efficacy score (imputed or observed) at the time point under consideration.

## Trimmed mean

As a supplemental analysis, the change from baseline in CHOP INTEND total score between treatment groups will be compared using the trimmed mean method to account for informative censoring due to death or withdrawal [Permutt and Li 2015].

Product: Nusinersen	Statistical Analysis Plan
Study: 232SM203	Version: 3.0 Final

The trimmed mean is an averaging method which eliminates a partial percentage of the smallest values before evaluating the standard mean of the given data. The trimmed mean difference can be interpreted as the mean difference of the top fraction of responses between the two groups. To do this, responses are ranked and subjects who have died or withdrew are considered as having worse outcomes than those who survived and completed the trial. To ensure that subjects who died or withdrew receive the lowest rank in response an arbitrary value of -999 will be assigned. The choice of this value does not impact the analysis results because these subjects are eventually excluded from the calculation of the trimmed mean statistics. Subject response scores in the two groups will then be ranked from the largest to the smallest separately. The top 100\*p% response scores from the two groups will be retained and the mean response difference is calculated as the trimmed mean statistics. Here, p is the minimum of the proportions of subjects who survived and completed the assessment in the two groups.

As a hypothetical example, using the 12 mg versus 50/28 mg with 232SM203 comparison, assume at the end of the study in which 75 subjects were randomized and dosed, the number of subjects who died or withdrew is 4 out of 50 (8.0%) in the nusinersen 50/28 mg group and 5 subjects out of 25 (20%) in the control group. The 9 subjects who died or withdrew in the two groups are assigned a response score of -999. The CHOP INTEND scores at Day 183 in the two groups are then ranked from largest to smallest separately. The top 80% of scores from each group will be retained and the mean difference is then calculated as the trimmed mean statistic.

Note that MI will not be used for trimmed mean approach. For subjects who don't have Day 183 data available (who do not withdraw from study or die), they will also be trimmed from analysis, i.e. they will also be assigned the arbitrary value of -999.

The p-value associated with the observed test statistic is then calculated using a reference distribution generated by the re-randomization procedure described below:

- 1. For all 75 subjects randomized in the ITT population, randomly assign subjects in a 50/25 ratio to treatment (nusinersen 58/28 mg or control) such that there are 50 subjects in the nusinersen 58/28 mg group and 25 in the control group. This can be done using simple random sampling without replacement. The seed used will be 5846894.
- 2. Calculate the trimmed-mean test statistic as described above using the random treatment assignment in Step 1
- 3. Repeat Steps 1 and 2 N times (N=10,000). As a result, N trimmed-mean statistics will be generated. The empirical distribution of the N trimmed-mean statistics will then serve as the reference distribution for p-value calculations.

Denote the observed trimmed mean statistic as T0. Once the reference distribution has been established, the p-value associated with the observed test statistic is calculated as proportion of simulated test statistics that are either greater than |T0| or less than - |T0|.

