## 3.6.2. External data

For CS3B, the efficacy set at Day 183 and Day 302 as defined for the final analysis of CS3B will be utilized.

The following table describes analysis sets for the historical data and how they will be referenced in the remainder of the document.

Table	1:	Analy	sis	set
-------	----	-------	-----	-----

Analysis Set Label	Description
CS3B Day 183 efficacy set	This is the 'Evaluable set for Day 183' referenced in the Final CS3B CSR. It consists of N=37 sham control and N=73 12 mg nusinersen participants.
CS3B Day 302 efficacy set	This is the 'Evaluable set for Day 302' referenced in the Final CS3B CSR. It consists of N=28 sham control and N=49, 12 mg nusinersen participants.
Matched Sham Set	Analysis set for main comparisons of higher dose versus sham control.
	Subset of the 37 sham control participants in the CS3B Day 183 efficacy set similar to higher dose 232SM203 participants and all higher dose participants in the ITT set.
Matched Sham Set (sensitivity)	Subset of the 37 sham control participants in the CS3B Day 183 efficacy set similar to all N=75 232SM203 participants in the ITT set.
Greedy matched set (sensitivity)	Set of CS3B sham and 232SM203 higher dose participants matched by greedy matching. Note that not all higher dose participants will have a match.

Page 20

Product: Nusinersen	Statistical Analysis Plan
Study: 232SM203	Version: 3.0 Final

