## 6.2. Use of Historical Data

The primary and some secondary endpoints will compare high dose to sham control. A total of N=37 are available from CS3B at Day 183. The following algorithm will be used to select the maximum number of Sham control subjects who are comparable at baseline to 232SM203 (N=75) based on two covariates: disease duration at informed consent, baseline CHOP INTEND total score. The algorithm will stop at a minimum of 20 participants.

[figure not shown]

[figure not shown]

Page 33

Page 34

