### Supplementary Analyses

In order to provide additional understanding of the treatment effect, two supplementary analyses will be performed on the primary endpoint. The first, in order to provide an estimate of the difference in CHOP INTEND using an ANCOVA model at each timepoint the MI dataset generated for the primary endpoint will be utilized. As a sensitivity analysis, this will be repeated using an ANCOVA model where the variance in each treatment group is estimated separately.

The second will utilize the following estimand which is described as the trimmed mean:

- Population: The ITT Set is considered and the treatment arm with the highest % of participants withdrawn by Day 183 is determined (labelled X). The same fraction is applied to the other treatment arm and the analysis is performed on (100-X) % of the ITT Set
- Variable: difference between treatments in the endpoint means in the (100-X) % subset of participants with the most favorable outcomes,
- Handling of intercurrent events: Due to the population definition, the intercurrent events of death or withdrawal from study are dynamically trimmed from the ITT Set. The assumption here is that any ICE is an equally bad outcome.
- Population level summary ANCOVA

These analyses are further described in Section in Section 6.1.

Product: Nusinersen
Study: 232SM203

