## Table 4: CHOP INTEND: Change from baseline to Day 183, accounting for mortality/dropout. Comparing the 50/28-mg Group to Study CS3B Sham Control

Туре	Analysis Method	Analysis Population: Further Notes	
Primary Analysis	Joint rank using multiple imputation (MI)	Matched Sham Set	
Sensitivity Analysis	Joint rank using multiple imputation (MI)	Matched Sham Set (sensitivity)	
	Joint rank using multiple imputation (MI)	Greedy matched set (sensitivity)	
	Adjustment of ranking criteria for JRT for withdrawals not due to death	Matched Sham Set	
	Adjustment of ranking criteria for JRT for permanent ventilation	Matched Sham Set	
	Subjects who died will be excluded from the MI model	Matched Sham Set	
	Joint rank using multiple imputation (MI)	Matched Sham Set. Data truncated to only include data up to Day 183 (inclusive).	
	Joint rank using Jump to Control MI	Matched Sham Set	
	Rank based implementation of joint rank method + MI	Matched Sham Set	
	Joint rank test using multiple imputation (MI), ANCOVA model not assuming equality of variance	Matched Sham Set	
	Joint rank using multiple imputation (MI) by disease duration	Matched Sham Set	
	Joint rank using multiple imputation (MI) by baseline CHOP INTEND	Matched Sham Set	
Supplementary Analysis	Trimmed mean	Matched Sham Set	

Product: Nusinersen

Study: 232SM203

Page 40

Endpoint and Comparison	Analysis Method	Analysis Population: further notes
Supplemental analysis		
Difference (50/28mg- Matched Sham Control) in change in CHOP INTEND from baseline by visit	ANCOVA using MI	Matched Sham Set
Difference (50/28mg- Matched Sham Control) in change in CHOP INTEND from baseline by visit	ANCOVA using MI (Not assuming equality of variances)	Matched Sham Set

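### The only p-value procedure given for the trimmed mean permutes the 75 randomised participants, but the analysis compares 50/28 mg with matched CS3B sham controls, none of whom are among those 75

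*SAP*

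**What the plan says.** All references are to the Part B infantile-onset SAP.

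- **Where the analysis is planned.** Table 4 in Section 6.3.1 ("Comparing the 50/28-mg Group to Study CS3B Sham Control") carries the row "Supplementary Analysis Trimmed mean Matched Sham Set". The tables for the other endpoints and for the 12 mg comparisons list no trimmed mean.
- **Who is analysed.** Table 1 in Section 3.6.2 defines the Matched Sham Set as a subset of the CS3B shams "similar to higher dose 232SM203 participants and all higher dose participants in the ITT set". Section 6.2 adds "A total of N=37 are available from CS3B at Day 183" and sets a floor of 20 matched shams.
- **How the p-value is obtained.** Section 6.1, Trimmed mean, Step 1: "For all 75 subjects randomized in the ITT population, randomly assign subjects in a 50/25 ratio to treatment", "such that there are 50 subjects in the nusinersen 58/28 mg group and 25 in the control group". The statistic is then recalculated over 10,000 reassignments with a fixed seed, and the two-sided p-value is read from that distribution. No version is given for the sham comparison.
- **Who is in the ITT Set.** Section 3.6.1 limits it to participants randomised and dosed in 232SM203.
- **How much is trimmed.** Section 6.1: "Here, p is the minimum of the proportions of subjects who survived and completed the assessment in the two groups". Section 6.3.1, Supplementary Analyses: "The ITT Set is considered and the treatment arm with the highest % of participants withdrawn by Day 183 is determined (labelled X".

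**The concern.** A permutation p-value is meaningful only if the permuted data are the data that produced the statistic. Here the observed trimmed-mean difference (T0 in the SAP) uses 50/28 mg and sham participants, while the reference distribution is built from 50/28 mg and 12 mg participants. The control group differs, and so does its size, which is fixed at 25 in the procedure but lies between 20 and 37 in the analysis. A programmer following the steps would report a p-value that does not test the comparison in Table 4. A programmer who adapted them would be choosing the pool and group sizes without a prespecified rule.

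Section 6.3.1 adds to the uncertainty. The population it names contains no sham participants, and its trimming fraction is worded as a percentage withdrawn, whereas Section 6.1 counts everyone who did not both survive and complete the assessment.

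**Working it through.** **1. The plan's own figure.** The SAP gives no figure for the trimmed mean. The only computed one for this comparison is the power in Section 2.3: at least about 99% for 50 versus 20, difference 24, SD 8.8, two-sided 0.05.
- SE = 8.8 × √(1/50 + 1/20) = 2.33, and 24/2.33 = 10.3 standard errors, so two-sample power exceeds 0.999.
- A simplified joint-rank simulation (no covariates or imputation), with sham survival assumed at 0.5, 0.6 and 0.7 and the higher dose 0.23 above it, gives 0.994, 1.00 and 1.00.

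The stated power reproduces.

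**2. The two pools side by side.**

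| Group | In T0 (Table 4) | In the reference distribution (Section 6.1) |
|---|---|---|
| 50/28 mg | 50 | 50 |
| 12 mg | 0 | 25 |
| CS3B sham | 20 to 37 | 0 |
| Total | 70 to 87 | 75 |

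Only the control side differs; the 50 higher-dose participants are common to both.

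**3. Type I error, no effect, before trimming.** Assume a common SD in all groups and a normal approximation. The true SE of the difference relative to the reference SE is

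r = √(1/50 + 1/n) / √(1/50 + 1/25), where n is the number of matched shams,

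and the actual size at nominal 0.05 is 2 × [1 − Φ(1.96/r)].

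| n | r | 1.96/r | Actual size |
|---|---|---|---|
| 20 | √0.0700/√0.0600 = 1.080 | 1.815 | 0.070 |
| 25 | 1.000 | 1.960 | 0.050 |
| 30 | √0.0533/√0.0600 = 0.943 | 2.079 | 0.038 |
| 37 | √0.0470/√0.0600 = 0.885 | 2.214 | 0.027 |

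**4. The same check with the trimmed-mean statistic, by simulation.** There were 400 data sets of 200 permutations per scenario. Higher dose and sham had the same distribution. The 12 mg group was either equal or 4.5 points lower (Section 2.3's assumed gain). Survival was assumed at 1.00 for all, or 0.90 with 0.87 for 12 mg.
- Section 6.1 pool: size 0.055 to 0.075 with 20 shams and 0.015 to 0.028 with 37.
- Matched Sham Set pool: 0.033 to 0.055.

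Each figure carries a simulation error of about ±0.02. The pattern agrees with step 3.

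**5. At the design effect.** The means were 24 (higher dose), 19.5 (12 mg) and 0 (sham), SD 8.8. Higher-dose survival was assumed at 0.95 or 0.85, with sham 0.23 lower and 12 mg 0.03 lower. The 5% critical value of the absolute statistic, averaged over 40 data sets of 400 permutations, is:
- Section 6.1 pool: about 4.8 to 5.7.
- Matched Sham Set pool: about 8.9 to 10.1 with 20 shams, and 8.5 to 9.6 with 37.

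An observed difference near 24 exceeds all of these.

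**6. Trimming fraction.** Section 6.1's worked example counts deaths and withdrawals together: 4/50 = 8% and 5/25 = 20%, so the top 80% of each arm is kept. The same section also trims participants who neither died nor withdrew but lack a Day 183 score. Section 6.3.1's percentage withdrawn does not plainly cover deaths or these participants.

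**The case against.** The strongest reply is that the figures 75, 50 and 25 are carried over from the worked example just above the procedure, which is labelled hypothetical and uses the 12 mg comparison. The SAP also uses ITT loosely for sham comparisons elsewhere: Section 6.3.1 runs the imputation model that excludes deaths on the ITT population where Table 4 says Matched Sham Set. On this view it is a wording slip that any statistician would correct. That is probably how it arose, but the hypothetical label belongs to the example. The numbered steps carry their own seed and repetition count, and no sham version exists.

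Several stronger readings are tempting, and the documents do not support them.

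- **That the reference distribution is always too narrow, so the p-value is always too small.** This holds under no effect with 20 shams. At 25 the sizes agree, and above 25 the test is conservative. Section 6.2 seeks the maximum number of comparable shams, so either direction is possible.
- **That critical values differing by nearly a factor of two could change the conclusion.** That gap arises under a true 24-point effect, which itself widens the matched-set permutation distribution. An observed difference near 24 clears both cut-offs.
- **That deaths coded −999 would enter the mean.** Section 6.1 says these participants are excluded from the trimmed mean, and the Section 6.3.1 estimand says deaths and withdrawals are both trimmed. This is a conflict of wording to settle, not a demonstrated error.
- **That simple rather than stratified permutation is a mistake.** The sham controls were not randomised against the higher dose, so there is no allocation scheme to reproduce. Permuting within disease-duration strata, or adding a bootstrap interval, is a preference.

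**Conclusion.** The point holds. Followed as written, Section 6.1 takes the p-value for T0 from a pool that omits every control in T0 and includes 25 participants outside the comparison. That is not a valid permutation p-value for Table 4's analysis. With no effect and before trimming, its type I error at nominal 0.05 runs from about 0.07 with 20 matched shams, through 0.05 with 25, to about 0.03 with 37. These values assume a common SD and a normal approximation. The simulations with trimming also rest on assumed survival rates, because Section 2.3 gives only differences.

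Section 6.3.1's population label conflicts with Table 4, and its trimming fraction needs to be reconciled with Section 6.1.

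The consequence is limited. The trimmed mean is supplementary and absent from the Table 2 testing sequence, and at the assumed 24-point effect its conclusion is unlikely to change. What is affected is a supportive p-value for the primary endpoint, not the confirmatory result.

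**What to change.** - **Section 6.1, Step 1:** for the Table 4 analysis, permute labels within the Matched Sham Set, keeping its actual numbers of higher-dose and sham participants.
- **Section 6.1, Step 2:** state that the trimming fraction is recomputed in each permutation.
- **Section 6.1, description:** call it a permutation test of non-randomised groups, resting on exchangeability under the null and not on the allocation scheme.
- **Section 6.3.1:** change the population to the Matched Sham Set. Define X as the larger of the two arms' percentages who died, withdrew or had no Day 183 score, to agree with Section 6.1.
- **Arm label:** Step 1 names the higher-dose arm as 58/28 mg, while the rest of the SAP says 50/28 mg; the two must be reconciled.

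The cost is a few lines of SAP text and a small change to the permutation code. No new data are needed.
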